## **End date of a treatment cycle and cycle length**

The cycle length (days), i.e., duration of a treatment cycle, will be calculated as follows: for each cycle, cycle length = the end date of cycle – the start of cycle + 1.

The start date of a treatment cycle is defined as the first azacitidine administration within the cycle, if azacitidine is administered within the cycle (in case azacitidine is not administered within the cycle, a cycle starts at 7 days before the date of MBG453 administration within the cycle; in case neither azacitidine or MBG453 is administered within the cycle, a cycle starts at the date of first venetoclax administration within the cycle as per 28-day/cycle).

The end date of a treatment cycle = the start date of next treatment cycle – 1. If it is the last cycle, the end date of last cycle is the end date of last initiated, which is calculated as above.

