6.5.3 Dose modifications

For subjects who do not tolerate the protocol-specified dosing schedule, dose interruptions (for MBG453, azacitidine and venetoclax), and/or dose reductions (azacitidine and venetoclax only) are either recommended or mandated in order to allow subjects to continue the study treatment.

Guidelines for permanent treatment discontinuation is mandatory for specific events indicated as such in [Table 6-5](#) and [Table 6-6](#).

Dose interruption at the start of a new treatment cycle

In subjects who have achieved CR, CRI or MLFS and have Grade 4 neutropenia and/or Grade 4 thrombocytopenia lasting at least 7 days dosing of both venetoclax and azacitidine should be interrupted until resolution to \leq Grade 2 or to a clinically significant threshold per investigator assessment ([NCCN 2021](#)). In case of a prolonged cytopenia, close blood monitoring is required, and the investigator should consider repeating bone marrow examination to determine if morphologic remission (CR, CRI, MLFS) is ongoing. Administer growth factors if indicated ([NCCN 2021](#)). MBG453 should not be administered during the dose interruption. After resolution, dosing of both azacitidine and venetoclax should be resumed on the same day with dose modification for venetoclax as specified in [Table 6-6](#). The first day dosing is resumed will be considered as D1 of the new treatment cycle and MBG453 will be administered on Day 8 of the new cycle. In cases in which venetoclax and azacitidine have been permanently discontinued and the patient remains on MBG453, then in subjects who have achieved CR, CRI or MLFS and have Grade 4 neutropenia and/or Grade 4 thrombocytopenia dosing of MBG453 should be interrupted until resolution to \leq Grade 2. The first day dosing with MBG453 is resumed will be considered D8 of the new cycle.

Dose modifications for MBG453

Dose modifications for MBG453 will be done according to ASCO guidelines about management of immune-related AEs ([Schneider et al 2021](#)).

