Additionally, the guidance indicated in [Table 6-5](#) below, provides instructions for infusion reaction, immune-related adverse events not covered by ASCO guidelines and a general guideline for non-hematologic non-immune-related toxicities that are clinically significant per investigator judgement and possibly attributable to the investigational drug. This general guideline will not apply in case of non-hematologic non-immune-related toxicities that are attributable to azacitidine, venetoclax and AML and its complications.

Deviations to dose interruptions, reductions and/or permanent discontinuations outlined in [Table 6-5](#) are not allowed.

Administration of MBG453 may be delayed due to toxicities. A scheduled dose may be delayed within a cycle by up to 14 days. If a dose cannot be administered within the planned window within the cycle, then the dose should be skipped. Next scheduled dosing may resume once the adverse event has resolved to \leq Grade 1 or baseline per the next planned treatment cycle. Dose reductions for MBG453 are not allowed.

Overall, for adverse events of potential immune-related etiology (irAE) that do not recover to \leq Grade 1 or baseline at a dose of immunosuppression of \leq 10 mg/day prednisone or equivalent (or as indicated in [Table 6-5](#)) within 12 weeks after initiation of immunosuppressive therapy, MBG453 must be permanently discontinued.

Table 6-5 Criteria for dose interruption and re-initiation of study drug MBG453 for adverse drug reactions

Worst Toxicity Grade (CTCAE v5.0)	Recommended Dose Modifications
Infusion Reaction	
Grade 1	Decrease infusion rate until recovery
Grade 2	
Stop infusion
 
Before restarting - pre-medicate according to local institutional guidelines.
 
Restart infusion at 50% of previous rate under continuous observation. Ensure that there is a minimum observation period of 1 hour prior to restarting the infusion(s). If the AE recurs at the reinitiated slow rate of infusion, and despite oral pre-medication*, then discontinue MBG453

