	Subsequent occurrences in next treatment cycles after achieving remission (CR, CRi, MLFS) and lasting at least 7 days	Delay subsequent treatment and monitor blood counts. Administer G-CSF if clinically indicated for neutropenia. Once the toxicity has resolved to Grade 1 or 2, resume venetoclax therapy at the same dose with a duration reduced by 7 days for each subsequent treatment cycle
Blood chemistry changes suggestive of TLS	-	Withhold treatment. If the event is resolved within 48 hours of last dose, treatment with venetoclax can be resumed at the same dose.

Event	Occurrence	Action
Events of clinical TLS or blood chemistry changes requiring more than 48 hours to resolve	-	Withhold treatment. Treatment should be resumed at a reduced dose (per the investigator discretion). When resuming treatment after interruption due to TLS, the instructions for prevention of TLS should be followed.
Grade 3 or 4 non-hematologic toxicities	First occurrence	Withhold treatment. Once the toxicity has resolved to Grade 1 or baseline level, venetoclax therapy may be resumed at the same dose.
	Subsequent occurrences	Withhold treatment. Treatment should be resumed at a reduced dose (per the investigator discretion).

Permanent discontinuation of study treatment

If the study treatment (i.e. MBG453 + azacitidine + venetoclax) is interrupted for toxicities and the start of the subsequent study treatment cycle is delayed for more than 42 consecutive days (measured from the intended start date of the new cycle (Day 29 of the previous cycle) in absence of clinical benefit for the patient per investigator assessment, the subject should be discontinued from study treatment.

At any time during the study, patients unable to tolerate one or two of the study treatment drugs may continue study treatment with only the tolerated drug(s) provided the subject benefits per investigator's judgement.

These dose changes must be recorded on the appropriate CRF.

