During the course of the study visits, test and/or procedures should occur on schedule whenever possible. A visit window of \pm 3 days is allowed for study procedures (including treatment administration). If MBG453 administration on Day 8 is delayed within a cycle due to toxicities, visit assessments for Day 8 should be shifted accordingly or occur on Day 22, in case of no administration. See [Section 6.1](#) for details on study treatment. A window of \pm 8 days from the planned visit date is allowed for BMA procedures. Further, a maximum of 8 days is allowed between BMA efficacy, extramedullary disease assessment (if applicable) and hematology assessments of the same visit.

Note: If a treatment cycle is delayed at any time during the study, all study visits and safety and efficacy assessments should continue according to the appropriate number of calendar days measured from Day 1 of the previous cycle, or more often if clinically indicated. When treatment is resumed, the first day of azacitidine and venetoclax administration will be considered as D1 of the new treatment cycle and visit schedule will be shifted accordingly.

On PK collection days the windows are provided in [Section 8.5.2](#). Subjects who discontinue the study treatment for any reason should be scheduled for an end of treatment (EOT) visit within

14 days from the decision to permanently discontinue study treatment, at which time all of the assessments listed for the EOT visit will be performed.

Patient Reported Outcomes must be completed before any clinical assessments are performed at any given visit.

For post-treatment follow-up and survival information, please refer to [Section 8.3.1](#), [Section 9.1](#).

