### **End date of the last cycle initiated**

The end date of the last cycle initiated is the maximum date between:

- The planned end date (Day 28) of the last cycle initiated when the last non-zero dose of any last component of the study treatment (MBG453 or azacitidine or venetoclax) is administered,
- The actual date of the last administration of a non-zero dose of any last component of the study treatment.

The end date of the last cycle initiated (Day 28 or beyond) will be applicable even if this date goes beyond the data cut-off date (i.e., it should not be truncated to the date of data cut-off).

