## **Duration from first to last cycle initiated to calculate dose intensity and the relative dose intensity**

For the calculation of the dose intensity and relative dose intensity, the duration in days from first to last cycle initiated will be calculated as follow: end date of the last cycle initiated - date of first administration of study treatment (combination) + 1.

Thus, this derivation will be irrespective of date of death or last contact date (i.e., it should not be truncated to the date of death or date of last contact).

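### In cycles given as venetoclax plus MBG453 without azacitidine, SAP 5.1 dates cycle start from the MBG453 infusion, so a permitted MBG453 delay distorts cycle length by up to 14 days, and the dose-intensity denominator only if that cycle is the last

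*SAP*

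**What the plan says.** SAP Section 5.1 (End date of a treatment cycle and cycle length) starts a cycle at its first azacitidine dose. For cycles without azacitidine it says: "in case azacitidine is not administered within the cycle, a cycle starts at 7 days before the date of MBG453 administration within the cycle". The first venetoclax dose is used only when neither azacitidine nor MBG453 was given. The end of any cycle but the last follows from the next start: "The end date of a treatment cycle = the start date of next treatment cycle", minus one day.

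For dose intensity, the duration is "end date of the last cycle initiated - date of first administration of study treatment (combination) + 1" (SAP 5.1). The end of the last cycle is the later of "The planned end date (Day 28) of the last cycle initiated" and the last non-zero dose of any component.

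Protocol Section 6.5.3 says of MBG453: "A scheduled dose may be delayed within a cycle by up to 14 days". If that window is missed, the dose is skipped. Section 8 then moves the Day 8 assessments with the delayed dose, or to Day 22 if there is no dose. Section 8 defines a new Day 1 separately, for a delayed cycle: "the first day of azacitidine and venetoclax administration will be considered as D1 of the new treatment cycle".

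Venetoclax plus MBG453 is a permitted regimen. Protocol Sections 3 and 6.5.3 let patients go on with only the drugs they tolerate, and the estimand in SAP 2.5.1 includes combinations of two of the three drugs.

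**The concern.** The fallback is correct only if MBG453 was given on Day 8. A dose given on Day 22 puts the derived start on Day 15, although daily venetoclax may have begun the cycle on Day 1.

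The rule also contradicts itself. Take one azacitidine-free patient with an unchanged venetoclax calendar. If MBG453 is skipped, the cycle starts at the first venetoclax dose, Day 1. If MBG453 is given 14 days late, the same cycle starts on Day 15.

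At stake are the exposure tables of SAP 2.4.1. The preceding cycle would appear prolonged, which reads as a treatment delay that did not happen. The cycle-length table carries more weight because SAP version 2.0 dropped the cycle-delay analysis and added cycle length by cycle. If the last cycle is affected, the dose intensity of all three drugs is understated.

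**Working it through.** **The plan's own figures.** The SAP gives no number for this rule. Its only numerical use of the denominator is the venetoclax example in 5.1, over 4 × 28 = 112 days:
- Unadjusted: 30200 / 112 × 28 = 7550 mg per 28 days.
- Adjusted: 38600 / 112 × 28 = 9650 mg per 28 days.
- Planned: 44200 / 112 × 28 = 11050 mg per 28 days.
- Relative: 9650 / 11050 = 87.33%.

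All agree with the SAP.

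**Inputs.** Planned cycle of 28 days; MBG453 on Day 8; delay of up to 14 days (Protocol 6.5.3); start, end and denominator rules from SAP 5.1; cycle-length categories <35, 35 to <42, 42 to <56, 56 to <70 and ≥70 days, and planned MBG453 intensity of 400 or 800 mg per 28 days (SAP 2.4.1).

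**Set-up.** Six true 28-day cycles start on study days 1, 29, 57, 85, 113 and 141. Azacitidine is absent from cycle 3 on, venetoclax continues on schedule, and later cycles keep the original calendar (an assumption). The true denominator is 168 days.

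**Delay in cycle 4 only.**
- MBG453 planned: 85 + 7 = day 92. Given: 92 + 14 = day 106.
- Derived start of cycle 4: 106 − 7 = day 99.
- Cycle 3: 98 − 57 + 1 = 42 days. Cycle 4: 112 − 99 + 1 = 14 days.
- Denominator: (141 + 27) − 1 + 1 = 168 days, so no error.

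**Delay in cycle 6 (the last) only.**
- MBG453 planned: 141 + 7 = day 148. Given: day 162. Derived start: day 155.
- Cycle 5: 154 − 113 + 1 = 42 days.
- Derived Day 28: 155 + 27 = day 182. Denominator: 182 days against 168, so +14.

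| MBG453 delayed 14 days in | Derived cycle lengths | Denominator | Error |
|---|---|---|---|
| cycle 4 only | 28, 28, 42, 14, 28, 28 | 168 | 0 |
| cycle 6 (last) only | 28, 28, 28, 28, 42, 28 | 182 | +14 |
| every azacitidine-free cycle | 28, 42, 28, 28, 28, 28 | 182 | +14 |
| cycle 6, azacitidine given throughout | 28, 28, 28, 28, 28, 28 | 168 | 0 |

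In the first three rows, one cycle moves from the <35-day to the 42 to <56-day category.

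**Effect on relative dose intensity when the last cycle is affected.** For n full MBG453 doses in n cycles the true value is 1.00. The derived value is 28n / (28n + 14) = 2n / (2n + 1).

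| Cycles | Denominator, true → derived (days) | Overstatement | Derived value |
|---|---|---|---|
| 2 | 56 → 70 | 25.0% | 0.800 |
| 4 | 112 → 126 | 12.5% | 0.889 |
| 7 | 196 → 210 | 7.1% | 0.933 |
| 12 | 336 → 350 | 4.2% | 0.960 |
| 24 | 672 → 686 | 2.1% | 0.980 |

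**The case against.** The strongest reply is that counting back from MBG453 has protocol support. Protocol 6.5.3 covers patients who have stopped venetoclax and azacitidine for good and resume MBG453 after a cytopenia interruption: "The first day dosing with MBG453 is resumed will be considered D8 of the new cycle". Seven days earlier is Day 1, exactly as in the SAP. This stands. A reader might infer that every azacitidine-free cycle is misdated, but the documents do not support that for MBG453-only cycles resumed after cytopenia.

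A reader might also infer that dose-intensity denominators are wrong in general. They are not. The denominator runs from first dose to the end of the last cycle and does not sum cycle lengths, so earlier shifts cancel.

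The 42- and 14-day split depends on the next cycle keeping its calendar. If later cycles followed the delayed dose, the second figure would be 28, and the derived start could be read as a consistent re-anchoring. The protocol does not say outright how Day 1 is set after a non-haematological MBG453 delay without azacitidine. Its wording still points to an unchanged Day 1: the delay is placed inside the cycle, a missed dose is skipped, and only the Day 8 assessments move.

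Last, venetoclax is an imperfect anchor. It can be withheld on its own (Protocol Table 6-6), and with daily dosing the first dose of a cycle can be identified only if the boundary is recorded. The first part stands and shapes the fix. The second applies equally to the SAP's existing venetoclax fallback.

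**Conclusion.** The point holds for cycles that contain venetoclax and MBG453 but no azacitidine, when MBG453 is delayed and not skipped. There the derived start is late by the length of the delay, up to 14 days. The preceding cycle appears up to 14 days too long. The delayed cycle appears correspondingly short if the calendar is kept. The denominator is up to 14 days too long, always in the direction of understating intensity, only when the delayed cycle is the last one initiated.

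The result rests on venetoclax having started the cycle on time and on Day 1 not being reset by an MBG453 delay. The 14-day bound leaves out the ±3-day visit window in Protocol Section 8, which could widen the error to about 17 days (14 + 3).

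The importance is minor. Cycle length and dose intensity are descriptive, the primary CR endpoint does not use them, and the number of patients affected is not given and is probably small.

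**What to change.** Reword the cycle-start sentence in SAP 5.1 as an ordered rule:
1. The first azacitidine dose in the cycle.
2. If there is none and both other drugs were given, the earlier of the first venetoclax dose recorded for that cycle and the MBG453 date minus 7 days.
3. The MBG453 date minus 7 days alone only when MBG453 is the sole drug in the cycle.
4. If only venetoclax was given, its first dose, as now.

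Taking the earlier date also covers a late venetoclax start. If both drugs are late, an error equal to the shorter delay remains. The rule assumes that the eCRF assigns venetoclax records to cycles.

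Align the text under Date of last exposure to study treatment component (SAP 5.1), which defines cycle start by azacitidine only and has no fallback.

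The cost is one reworded sentence, one aligned definition and a small programming change. No new data and no change to treatment rules are needed.

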## **Study day**

The study day describes the day of the event or assessment date, relative to the reference start date (start date of study treatment).

The study day is calculated as follows:

- The date of the event (visit date, onset date of an event, assessment date etc.) – reference start date + 1 if event is on or after the reference start date;
- The date of the event (visit date, onset date of an event, assessment date etc.) – reference start date if event precedes the reference start date.

The reference start date for safety assessments (e.g. adverse event onset, laboratory or ECG assessment, vital sign measurement etc.) is the start of study treatment. The same reference start date will be used for efficacy (e.g. response assessment, time-to-event endpoints) and patient-reported outcomes (PRO).

The study day will be displayed in the data listings. If an event starts before the reference start date, the study day displayed on the listing will be negative.

## **Time unit**

A year length is defined as 365.25 days. A month length is 30.4375 days (365.25/12). If duration is reported in months, duration in days will be divided by 30.4375. If duration is reported in years, duration in days will be divided by 365.25.

## **Baseline**

For efficacy evaluations and PROs, the last non-missing assessment, including unscheduled assessments on or before the date of start of study treatment is taken as “baseline” value or “baseline” assessment.

For safety evaluations, the last available assessment including unscheduled assessments on or before the date of start of study treatment is taken as “baseline” assessment.

If subjects have no value as defined above, the baseline result will be missing.

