6.1.1 Investigational and control drugs

Table 6-1 Study Treatment

Investigational/ Combination Drug (Name and Strength)	Strength	Pharmaceutical dosage form and route of administration	Supply Type	Sponsor (global or local)
MBG453	100 mg in 1ml and/or 400 mg in 4 ml	solution in vial for i.v. infusion	Open Label	Sponsor (global)
Venetoclax	100 mg and/or 50 mg and/or 10 mg (or as per local supply)	tablet for oral use	Open Label	Sponsor (global) or provided locally (US)
Azacitidine*	as per local supply	solution for i.v. infusion or subcutaneous administration	Open Label	Provided locally

* Formulation for generic azacitidine as approved by local regulations

MBG453

MBG453 will be administered at a dose of 400 mg Q4W (safety run-in cohort 1) or 800 mg Q4W (safety run-in cohort 2 and expansion) via i.v. infusion over 30 minutes on Day 8 of every 28-day cycle.

If the alternative schedule is selected for azacitidine by the investigator, azacitidine and MBG453 will be given on the same day (day 8 of the 28-day cycle). Azacitidine should be administered first, followed by MBG453. The first dose of MBG453 should be administered after the subject has received at least 5 doses of azacitidine.

Further instructions for the preparation, dispensation, and administration of MBG453 are described in the Pharmacy Manual.

Venetoclax

Venetoclax film-coated tablets should be administered at a dose of 400 mg orally or corresponding reduced dose for concomitant use with P-gp inhibitors or moderate or strong CYP3A4 inhibitors (see [Table 6-3](#) and [Venclexta® \(Venetoclax\) USPI 2018](#)), once a day, on

each day of the 28-day cycle. Subjects should be instructed to swallow the tablets whole (tablets should not be crushed or broken), with water, at approximately the same time each day. The tablets should be taken with a meal (ideally at breakfast).

In Cycle 1, the dose of venetoclax will be ramped-up over a period of 3 or 4 days (C1D1 - C1D3 or C1D4) to achieve the dose of 400 mg per day (see [Table 6-2](#)), or corresponding reduced dose per day for concomitant with P-gp inhibitors or moderate or strong CYP3A4 inhibitors (see [Table 6-3](#) and [Venclexta® \(Venetoclax\) USPI 2018](#)). During the ramp-up period, venetoclax should be taken in the morning to facilitate laboratory monitoring. See [Section 8.4.4](#) for additional considerations during ramp-up and [Section 6.5.4.2](#). For guidance on prophylaxis and follow-up for suspected TLS.

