ECOG PS	X	X		X		X		X	X	X	X	X	X	X	X	X			
Hematology	X	X	X	X	X	X	X	X	X	X	X	X	X	X	X	X	every 12 weeks (aligned to time of response assessments) and if clinically indicated ⁵		
Chemistry	X ⁶	Pre-dose and at 7 hrs (+_1hr) post dose for each new dose during the venetoclax ramp-up and 24 hrs after reaching final dose (pre-dose of next dosing day), then on Day 1 of every subsequent Cycle, at EOT and unscheduled as clinically indicated																	
Coagulation	X	X		X		X		X	X	X	X	X	X	X	X	X			
Cytogenetics ⁷	X																		
Urinalysis (dipstick)	S	If clinically indicated																	
Thyroid function ⁸	X			X				X								at Cycle 8 Day 1 then every 3 cycles (Day 1) thereafter and as clinically indicated	X		

Period	Screening	Treatment												End of Treatment	Safety Follow-up	Post-Treatment Follow-up	Survival Follow-up		
Cycle		Cycle 1		Cycle 2		Cycle 3	Cycle 4	Cycle 5	Cycle 6	Cycle 7 (and subsequent cycles)									
Days	-28 to -1	D1	D8	D22	D1	D8	D22	D1	D8	D1	D8	D1	D8	D1	D8	EOT	30, 90, 150 days	Every 12 weeks	Every 12 weeks
Cytokines for safety (IFN-γ; IL-6, IL-1b, TNF-α)	X	Anytime for a suspected cytokine release syndrome, immediately after the AE, and one week after occurrence of AE																	
Virology hepatitis B and C	S	If clinically indicated																	
HIV serology (only if required per local regulation)	S																		
Additional hepatic tests in case of DILI ⁹	X ¹⁰	If clinically indicated																	
Serum Pregnancy test ¹¹	S	S ¹²													S				
Urine Pregnancy Test OR Serum Pregnancy Test ¹¹			S		S	S	S	S	S						monthly ¹³				
12-Lead ECG (triplicates) ¹⁴	X	X	X			X									X				
IRT-Drug dispensation for MBG453			X		X		X	X	X	X	X	X	X	X					
IRT-Drug dispensation for venetoclax ¹⁵		X		X		X	X	X	X	X	X	X							
MBG453 infusion		X		X		X	X	X	X	X	X	X	X	X					

Period	Screening	Treatment														End of Treatment	Safety Follow-up	Post-Treatment Follow-up	Survival Follow-up
Cycle		Cycle 1		Cycle 2		Cycle 3	Cycle 4	Cycle 5	Cycle 6	Cycle 7 (and subsequent cycles)									
Days	-28 to -1	D1	D8	D22	D1	D8	D22	D1	D8	D1	D8	D1	D8	D1	D8	EOT	30, 90, 150 days	Every 12 weeks	Every 12 weeks
Venetoclax administration		ramp-up (see Section 6.1.1) followed by daily administration																	
Azacitidine infusion		on Days 1- 7 of each Cycle OR on Days 1-6 and then on Day 8 of each cycle OR on Days 1-5 and then on Day 8 and Day 9 of each cycle																	

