8.4.4 Additional safety monitoring and considerations during venetoclax ramp-up

The dose of venetoclax will be ramped up over 3 or 4 days to achieve the daily dose of 400 mg (see [Table 6-2](#) for ramp-up procedure).

Blood chemistry should be taken pre-dose and at 7 hrs (+/- 1 hr) on during the ramp-up and approximately 24 hrs after reaching the final dose (pre-dose of the following dosing day, see [Table 8-1](#)).

Due to the known risk of TLS with venetoclax treatment, prior to first venetoclax dose on Cycle 1 Day 1, the subject should be provided with prophylactic measures including adequate hydration and anti-hyperuricemic agents and these measures should be continued during the ramp-up phase.

[figure not shown]
High risk patients may need additional measures like i.v. hydration and hospitalization, events should be managed per local guidelines.

Refer to [Section 6.5.4.2](#) for guidance on minimising the risk of TLS and procedures to be followed before initiation of a treatment cycle and during the treatment cycle.

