## **2.7 Safety analyses**

Safety analyses will be summarized for the safety set and by dose level of MBG453 (400 mg Q4W, 800 mg Q4W) and for all subjects (“All subjects” column).

Safety summaries (tables, figures) include only data from the on-treatment period with the exception of baseline data which will also be summarized where appropriate (e.g. change from baseline summaries). In addition, a separate summary for death including on treatment and post treatment deaths will be provided. In particular, summary tables for adverse events (AEs) will summarize only on-treatment events, with a start date during the on-treatment period (treatment-emergent AEs).

The overall observation period will be divided into three mutually exclusive segments:

1. Pre-treatment period: from day of subject’s informed consent to the day before first administration of study treatment
2. On-treatment period: from date of first administration of study treatment to 30 days after date of last administration of study treatment
3. Post-treatment period: any observation starting at day 31 after last administration of study treatment

An overall safety period will be defined from date of first administration of study treatment to 150 days after the last dose of MBG453.

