## **2.7.3 Laboratory data**

Grading of laboratory values will be assigned programmatically as per National Cancer Institute (NCI) Common Terminology Criteria for Adverse Events (CTCAE) version 5.0. The calculation of CTCAE grades will be based on the observed laboratory values only, clinical assessments will not be taken into account.

CTCAE Grade 0 will be assigned for all non-missing values not graded as 1 or higher.

For laboratory tests where grades are not defined by CTCAE version 5.0, results will be categorized as low/normal/high based on laboratory normal ranges.

For laboratory tests where grades are defined by CTCAE v5.0:

- Shift tables using CTCAE v5.0 grades to compare baseline to the worst on-treatment value

Liver function parameters of interest are total bilirubin, ALT, AST and alkaline phosphatase. The number (%) of subjects with worst post-baseline values as per Novartis Liver Toxicity guidelines will be summarized.

For hematology parameters, trends over time (baseline and on-treatment timepoints) will be displayed via boxplots and corresponding tables displaying the summary statistics will be produced.

All CTCAE Grade 3 or 4 laboratory toxicities will be listed.

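### The safety baseline goes by calendar date, so the 7-hour post-dose C1D1 chemistry becomes baseline while the pre-dose sample counts as on-treatment

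*SAP*

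**What the plan says.** SAP 5.1, under Baseline, sets the rule for safety data: "For safety evaluations, the last available assessment including unscheduled assessments on or before the date of start of study treatment is taken as" baseline. SAP 5.1 defines the start of study treatment as a date, that of the first non-zero dose of any component. Clock time and order relative to the dose do not enter.

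The Chemistry row of Protocol Table 8-1 requires samples "Pre-dose and at 7 hrs (+_1hr) post dose for each new dose during the venetoclax ramp-up", and Protocol 8.4.4 repeats the schedule. Ramp-up begins on C1D1. Protocol 6.1.1 adds: "During the ramp-up period, venetoclax should be taken in the morning to facilitate laboratory monitoring". Both C1D1 samples therefore carry the date of first dose.

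SAP 2.7, like Protocol 12.5.2, runs the pre-treatment period "to the day before first administration of study treatment" and then defines: "On-treatment period: from date of first administration of study treatment to 30 days after date of last administration of study treatment". SAP 2.7.3 plans: "Shift tables using CTCAE v5.0 grades to compare baseline to the worst on-treatment value". For liver parameters it adds: "The number (%) of subjects with worst post-baseline values as per Novartis Liver Toxicity guidelines will be summarized".

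**The concern.** Two date-only definitions meet on C1D1. The baseline rule admits a sample taken after dosing, and the on-treatment rule admits a sample taken before it. For chemistry, the protocol schedules one of each on that day. Read literally, the shift table then compares a post-dose baseline with a worst on-treatment value that may itself be pre-dose.

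Changes in laboratory values are part of a named secondary safety endpoint (Protocol Table 2-1, SAP Table 1-1). SAP 2.7.3 plans shift tables only for CTCAE-graded tests, so these tables are the main planned summary of change from baseline in chemistry. The 7-hour sample belongs to the monitoring that Protocol 8.4.4 sets around venetoclax ramp-up, in a section that cites the known risk of tumor lysis syndrome. Using that sample as baseline removes the first-dose change from the comparison.

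**Working it through.** The plan gives no figure to reproduce here. The check applies the definitions to every possible set of grades.

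**Inputs.** For one subject and one graded test, let p be the C1D1 pre-dose grade, h the C1D1 7-hour grade and l the worst later on-treatment grade, each from 0 to 4. That gives 5 × 5 × 5 = 125 patterns.

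**Rules.**

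- As written: baseline = h (SAP 5.1); worst on-treatment = max(p, h, l) (SAP 2.7).
- Ordered by dose: baseline = p; worst on-treatment = max(h, l).

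**Examples.**

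| p, h, l | Ordered by dose | As written | Effect |
|---|---|---|---|
| 0, 3, 1 | 0 to 3 | 3 to 3 | worsening hidden |
| 0, 1, 3 | 0 to 3 | 1 to 3 | worsening understated |
| 2, 0, 0 | 2 to 0 | 0 to 2 | false worsening |
| 2, 0, 3 | 2 to 3 | 0 to 3 | worsening overstated |

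**All patterns.**

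- h = p: 5 × 5 = 25 patterns. The two rules agree.
- h > p: 10 pairs × 5 values of l = 50 patterns. If l ≤ h, the table shows h to h and the worsening disappears. For each h there are h values of p and h + 1 values of l, so the count is 1×2 + 2×3 + 3×4 + 4×5 = 40. In the other 10, l exceeds h and the worsening is understated by h − p grades.
- h < p: 50 patterns by symmetry. If l ≤ p (40 patterns), nothing after the dose exceeds the pre-dose grade, yet the table shows a worsening from h to p. In the other 10, the worsening is overstated by p − h grades.

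Total: 25 + 40 + 10 + 40 + 10 = 125. In no pattern can the worst on-treatment grade fall below baseline, because the baseline record is itself on-treatment.

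**Does correcting baseline alone suffice?** No. For (2, 0, 0) it gives baseline 2 and worst max(2, 0, 0) = 2, so the table reads 2 to 2 instead of 2 to 0. The pre-dose record must also leave the worst on-treatment value.

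**Liver summary.** If post-baseline means after the baseline record, the 7-hour C1D1 values drop out of the worst post-baseline liver summary.

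**Subjects affected.** For each test, this is the share of subjects whose grade differs between the two C1D1 samples. The documents do not give that share. Purely as an assumption, 5% to 30% of the 85 subjects treated at 800 mg would be 0.05 × 85 = 4.25 to 0.30 × 85 = 25.5, or about 4 to 26. Nothing in the documents supports a particular value.

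**The case against.** Five points can be made for the plan.

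1. **Order of same-day samples.** Nothing visible requires clock times for chemistry, as the protocol does for PK draws, so it may be impossible to say which same-date sample is last. This does not rescue the rule. The two samples are separate scheduled time points, and their labels put the 7-hour sample last. If they could not be ordered, the rule would be undefined, which also needs correcting. Programmers might use a pre-dose flag in practice, but neither document says so.
2. **Nothing is lost from the on-treatment side.** In the (0, 3, 1) example, Grade 3 still appears as the worst on-treatment grade and in the Grade 3/4 listing. That is true. What is wrong is the baseline row, and hence the shift.
3. **The immunogenicity contrast.** SAP 2.2 takes the immunogenicity baseline before the first MBG453 dose, but that dose falls on Day 8, so a separate definition was needed anyway. This stands: the contrast shows only that the SAP uses dose-ordered wording elsewhere.
4. **Scope.** The pre-dose C1D1 hematology sample also counts as on-treatment, so a subject going from Grade 4 to a later worst of Grade 2 would show 4 to 4. This is correct. The overlap reaches beyond chemistry, although hematology has no scheduled post-dose C1D1 sample to displace its baseline.
5. **Importance.** The outputs are descriptive, the study has one arm, and the program has been terminated. This limits the consequence, but the final report will still contain these tables.

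**Conclusion.** The concern holds. Applied as written, SAP 5.1 and 2.7 give an incorrect chemistry shift for every subject and test whose CTCAE grade differs between the pre-dose and 7-hour C1D1 samples. The error runs in both directions and no net direction can be stated. The pattern counts describe the logic and are not an error rate; if few subjects change grade between the two samples, few entries are affected.

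The conclusion assumes that C1D1 sampling and morning dosing follow the protocol and that the SAP wording is programmed literally. The damage is confined mainly to the chemistry shift tables and the liver summary, with a lesser effect on hematology shifts that should show improvement. AE tables, DLT decisions, the Grade 3/4 laboratory listing and the CR analysis are unaffected. C1D1 ECGs are scheduled pre-dose, so the ECG baseline is not displaced. This should be corrected before the outputs are produced, but it does not threaten the trial's main conclusions.

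**What to change.** In SAP 5.1, define the safety baseline as the last non-missing assessment before the date and time of the first dose of any study treatment component. Where the C1D1 time is missing, use the sample labeled pre-dose in the schedule; failing that, use the last assessment before Day 1. State that post-dose C1D1 samples are post-baseline.

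In SAP 2.7, add a clause excluding the baseline record, and any other pre-dose C1D1 record, from the worst on-treatment value. The same clause deals with the hematology overlap.

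The cost is one sentence, one clause and a programming change. The scheduled time points already separate the two samples, so no new data are needed even if clock times were not collected. Because SAP 2.7 repeats the period definition in Protocol 12.5.2, the exclusion should also be recorded in SAP section 4, which currently lists no changes from the protocol.
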